2.6.3 Handling of missing values/censoring/discontinuations

Missing data

Patients who were unblinded prior to the scheduled timepoint will be considered non-responders from the time of unblinding up to Week 52.

Missing data for ACR20 response and other binary efficacy variables (e.g. monotherapy response of ACR50, ██████████, PASI90, etc.) for data up to Week 52 will be handled by Multiple Imputation (MI) if a subject neither discontinues the study treatment prematurely nor takes cDMARDs after week 36 but still has missing value for ACR20 (e.g., misses some visits). Details of the implementation is in [Section 6.2.2.4](#).

[figure not shown]
Multiple imputation (MI) is a simulation based approach where missing values are replaced by multiple Bayesian draws from the conditional distribution of missing data given the observed data and covariates, creating multiple completed data sets. These completed data sets can then be analyzed using standard methods. Within this analysis the ACR composites or PASI score will be imputed and response variables will be derived based on the imputed scores. In the multiple imputation analysis the response status will be imputed based on the individual treatment arm information.

[figure not shown]
Missing data for continuous efficacy endpoints due to missed or skipped visits will not be applied MI. Continuous variables (e.g. ACR20 components) will be analyzed using a mixed-effects repeated measures model (MMRM) which is valid for addressing missing value under the missing at random (MAR) assumption. As such, single-point imputation of missing data will not be performed (e.g. LOCF) nor employing MI. Details of the implementation is in [Section 6.2.1.2](#).

For analysis based on subset of subjects (i.e. Psoriasis, Enthesitis ██████████), a subject with missing baseline values will be excluded in the analysis.

For use of cDMARDs (including MTX) after Week 36, the start date and end date of cDMARDs use will be compared to the upper limit of the Week 36 analysis visit window (day 274). For partial or missing dates the following imputation rule will be used:

- If only date is missing (month and year are present), then for Concomitant Medication start date, use the first day of the month, for end date, use the last day of the month.
- If both month and date are missing, then for Concomitant Medication start date, use January 1st of the year, for end date, use December 31st of the year.
- If year, month and date are all missing, then for Concomitant Medication start date, no imputation will be applied but we assume the start date is before day 274. For Concomitant Medication end date, no imputation will be applied but we assume the end date is ongoing.

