4.1 Inclusion criteria

Patients eligible for inclusion in this study have to fulfill **all** of the following criteria:

- 1. Informed consent must be obtained before any assessment is performed.
- 2. Male or non-pregnant, non-lactating female subjects at least 18 years of age.
- 3. Diagnosis of PsA as classified by CASPAR criteria (see Appendix 1) and with symptoms for at least 6 months and with active PsA at baseline defined as ≥3 tender joints out of 78 and ≥3 swollen joints out of 76 (dactylitis of a digit, counts as one joint each).
- 4. Rheumatoid factor (RF) and anti-cyclic citrullinated peptide (CCP) antibodies negative at screening.
- 5. Diagnosis of active plaque psoriasis, with at least one psoriatic plaque of ≥ 2 cm diameter or nail changes consistent with psoriasis or documented history of plaque psoriasis.
- 6. Subjects with PsA should have taken NSAIDs for at least 4 weeks prior to randomization with inadequate control of symptoms or at least one dose if stopped due to intolerance to NSAIDs.
- 7. Subjects who are regularly receiving NSAIDs as part of their PsA therapy are required to be on a stable dose for at least 2 weeks before study randomization and should remain on a stable dose up to Week 52.
- 8. Subjects receiving corticosteroids must be on a stable dose of ≤10 mg/day prednisone or equivalent for at least 2 weeks before randomization and should remain on a stable dose up to Week 52.

Page 29

Amended Protocol Version 02 Clean

9. Subjects must have previously been treated with a cDMARD, including but not limited to MTX, with an inadequate response to therapy, or must have stopped treatment due to safety/tolerability problems after at least one administration of the cDMARD.

Subjects who are receiving a cDMARD will be allowed to enter the study only after cDMARD discontinuation and appropriate wash-out e.g. 4 weeks prior to randomization visit except for leflunomide, which has to be discontinued for 8 weeks prior to randomization unless a cholestyramine wash-out has been performed.

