2.5.2 Prior, concomitant and post therapies

Prior and concomitant medications will be summarized in separate tables by treatment group.

Prior medications are defined as treatments taken and stopped prior to first dose of study treatment. Any medication given at least once between the day of first dose of study treatment and the date of within 84 days after last dose will be a concomitant medication, including those which were started pre-baseline and continued into the period where study treatment is administered.

Medications will be presented in alphabetical order, by Anatomical Therapeutic Classification (ATC) codes and grouped by anatomical main group. Tables will show the overall number and percentage of subjects receiving at least one treatment of a particular ATC code and at least one treatment in a particular anatomical main group.

Significant prior and concomitant therapies and procedures will be summarized by primary system organ class and MedDRA preferred term.

The number and percentage of subjects receiving prior and concomitant psoriatic arthritis therapy will be presented by randomized treatment group as well as the reasons for stopping their therapies (primary lack of efficacy, secondary lack of efficacy, lack of tolerability, other). The number and percentage of subjects receiving the following three categories of prior or concomitant medications will be summarized separately in one table: cDMARDs, MTX and non-MTX cDMARDs. This is the list of cDMARDs: Sulfasalazine, Leflunomide, Cyclosporine, Methotrexate, azathioprine, minocycline and apremilast.

Prohibited medication is defined in section 5.5.8 of the protocol.

The number and rates of subjects taking Prohibited medication will be presented.

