2.6 Analysis of the primary objective

2.6.1 Primary endpoint

As the Primary objective of the study is to compare the efficacy of secukinumab **monotherapy** 300 mg s.c. with adalimumab **monotherapy** (40 mg s.c.) with respect to ACR20 at Week 52, the estimand of interest is the ACR20 response at week 52 in monotherapy patients who do not permanently discontinue study medication prematurely nor require rescue cDMARDS. The estimand will be evaluated in the FAS population by comparing the odds of response to each treatment (odds ratio). The primary efficacy endpoint is a composite endpoint. Clinical response, failure to permanently discontinue study medication prematurely, and lack of need for rescue medication will be required for a patient to achieve treatment success. The primary endpoint is the proportion of patients with **monotherapy** ACR20 response at Week 52 where **monotherapy** ACR20 response is defined as meeting the following three conditions:

- achieving American College of Rheumatology 20 (ACR20) response
- no permanent study treatment (Secukinumab or adalimumab) discontinuation before or at Week 50 (the last dosing visit)
- no use of cDMARDS (including MTX) after week 36 (regardless of the starting time of taking cDMARDS)

A patient who does not meet any of the three conditions above is regarded as a monotherapy non-responder.

The list of possible cDMARDS for criterion 3 are the following: sulfasalazine, leflunomide, cyclosporine, methotrexate, azathioprine, minocycline and apremilast.

The analysis of the primary efficacy endpoint will be based on the FAS subjects. Primarily, CRP will be used instead of ESR to calculate ACR response; ESR will only be used in the event CRP is missing.

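### SAP 2.6.3 sets no floor at first dose when it imputes cDMARD end dates, so a few washed-out records could turn a Week 52 responder into a non-responder

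*SAP*

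**What the plan says.** Condition 3 of monotherapy response (SAP 2.6.1) requires "no use of cDMARDS (including MTX) after week 36 (regardless of the starting time of taking cDMARDS"). SAP 2.6.3 puts this into practice: "the start date and end date of cDMARDs use will be compared to the upper limit of the Week 36 analysis visit window (day 274"). Incomplete dates are handled at three levels:

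- Day missing: "for Concomitant Medication start date, use the first day of the month, for end date, use the last day of the month".
- Day and month missing: "for Concomitant Medication start date, use January 1st of the year, for end date, use December 31st of the year".
- Everything missing: the start is taken to be before Day 274, and for the end, "For Concomitant Medication end date, no imputation will be applied but we assume the end date is ongoing".

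None of these steps asks for evidence of use on or after first dose, and none limits the imputed end date for a drug that was washed out.

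Other text bears on which records reach this rule:

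- Protocol 4.1, criterion 9: "Subjects must have previously been treated with a cDMARD". A patient still on one must stop and wash out before randomisation (4 weeks; 8 weeks for leflunomide unless cholestyramine is used).
- Protocol 6.3 sends drugs given before and during study treatment to the same Prior/Concomitant medications eCRF.
- SAP 2.5.2: "Prior medications are defined as treatments taken and stopped prior to first dose of study treatment". A drug given at least once from first dose onward is concomitant, even if it was started before baseline.

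Under the implementation steps in SAP 6.2.2.4, non-response for cDMARD use is set after multiple imputation. SAP 2.7 applies the same condition to PASI90, ACR50 and resolution of enthesitis.

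**The concern.** The date rule decides responder status in the primary endpoint. For a patient who was washed out as the protocol requires, an end date of ongoing, or 31 December after Day 274, contradicts what eligibility has already established.

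The split between prior and concomitant medication does not settle the matter, because sorting a record as stopped before first dose needs the very stop date that is missing. SAP 2.5.2 gives no rule for an undated stop. If the 2.6.3 assumption is used to do the sorting, an undated record becomes concomitant by assumption.

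A patient who took no cDMARD on study and met ACR20 could then be scored as a monotherapy non-responder in H1, and in the same way in H2, H3 and H5. Because non-response is imposed after imputation, nothing later in the analysis recovers that patient.

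**Working it through.** **Inputs.** Cut-off: study day 274 (SAP 2.6.3). Wash-out: 28 days, or 56 for leflunomide without cholestyramine (Protocol 4.1 and Table 5-2). ACR20 rates 62% and 50%, 425 per arm, two-sided 0.05, stated power 94% (Protocol 9.7, SAP 3). The share f of responders affected is not in the documents and is assumed equal in both arms. Day 1 is taken as the day of randomisation.

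**Cut-off.** SAP 6.1 gives the upper limit of the Week 36 window as 0.25×36×7 + 0.75×40×7 + 1 = 63 + 210 + 1 = 274, as stated. Day 274 is first dose plus 273 days.

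**Wholly missing end date.** Use is taken as ongoing, so it passes Day 274 whatever the date of first dose. The only protection is that the record is classed as prior, and the SAP does not say how that is decided without a stop date.

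**Year-only end date, year of first dose.**
- The study day of 31 December is (31 December − Day 1) + 1. It exceeds 274 only if Day 1 is at least 274 days before 31 December, that is, on or before 1 April.
- A stop in the same year is 1 January at the earliest. With a 28-day wash-out, Day 1 is then 29 January at the earliest; with 56 days, 26 February.
- The exposed first-dose dates are 29 January to 1 April (63 of 365 days, 17%) or 26 February to 1 April (35 days, 10%).

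**Year-only end date, earlier year.** 31 December of an earlier year falls before Day 1. No effect.

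**Month-and-year end date.** The worst case is a stop on the 1st of a 31-day month with Day 1 on the 29th. The imputed end is the 31st, which is study day 3. No effect.

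**Power.** With pooled variance under the null, power = Φ[(Δ − 1.96·SE0)/SE1].

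Plan's figure: Δ = 0.12, SE0 = √(2×0.56×0.44/425) = 0.03405, SE1 = √((0.62×0.38 + 0.50×0.50)/425) = 0.03380. Then z = (0.12 − 0.06674)/0.03380 = 1.576 and power is 94.2%, which reproduces the stated 94%.

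Multiplying both rates by (1 − f):

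| f (assumed) | Rates | Difference | Responders lost per arm (425 × rate × f) | Power |
|---|---|---|---|---|
| 0 | 62.0% vs 50.0% | 12.0 points | 0 | 94.2% |
| 1% | 61.4% vs 49.5% | 11.9 | 2.6 and 2.1 | 93.8% |
| 2% | 60.8% vs 49.0% | 11.8 | 5.3 and 4.2 | 93.3% |
| 5% | 58.9% vs 47.5% | 11.4 | 13.2 and 10.6 | 91.6% |
| 10% | 55.8% vs 45.0% | 10.8 | 26.4 and 21.2 | 88.4% |

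**The case against.** The best defence is that the partial-date rules are worded for concomitant medication, and SAP 2.5.2 puts a drug stopped before first dose outside that class. This stands for any record known to have stopped. It does not reach an undated stop, for the reason given above.

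There are also safeguards outside the rule:

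- Table 6-1 schedules a wash-out evaluation and a history of previous PsA therapies at screening.
- Reasons for stopping prior PsA therapy are to be tabulated, and a recorded reason is evidence that the drug stopped.
- Protocol 8.1 calls for full verification of eligibility and of data used for the primary variable, and Protocol 8.3 provides for queries before lock.

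These should make such records rare, above all a year-only stop within months of first dose at a site that had to confirm a 4-week wash-out. But the SAP does not say that any of these sources overrides the date rule. The eCRF itself is not available, so how often an undated historical record would enter the derivation cannot be established.

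Assuming continued use is also the cautious choice for a monotherapy endpoint, since condition 3 counts use whenever it began. That is a good reason to keep the assumption where nothing documents a stop. It is no reason to apply it against a documented wash-out.

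A reader might infer that every patient is exposed because every patient has had a cDMARD. The documents do not support that: the error needs an incomplete stop date, one of the seven drugs listed in SAP 2.6.1, and one of the two patterns above.

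**Conclusion.** The gap is real, narrow and minor. Followed literally, SAP 2.6.3 can misclassify a washed-out responder in the wholly missing case and in the same-year, year-only case, and nowhere else.

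The size rests on an assumed share. Up to 5% of responders affected leaves ACR20 power at 91.6% or more, and no figure in the documents suggests that the share is that high.

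Two stronger conclusions do not follow. First, how completely a pre-randomisation drug is dated should not depend on the arm assigned later, so there is no expected bias toward either drug and no inflation of type I error, only dilution. Second, a reader of SAP 2.7 alone might infer that all of such a patient's post-baseline HAQ-DI data would be lost. The implementation steps in SAP 6.2.1.2 confine the loss to data collected after cDMARD use after Week 36.

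**What to change.** Add to SAP 2.6.3: where a cDMARD is documented as previous therapy, or as stopped or washed out before randomisation (eligibility, wash-out evaluation or previous-therapy records), an imputed end date may not be later than the day before first dose. Keep the ongoing assumption for records with no such documentation, including those with both dates missing. Before database lock, query every record of a listed cDMARD with an incomplete stop date.

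A looser rule that assumed ongoing use only where a record is ticked as ongoing or starts after first dose would go too far. It could miss a cDMARD really taken on study with both dates blank, or one begun before the study and never stopped.

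The cost is one derivation rule and some data cleaning. With the cap in place and the records documented, f is 0 and power stays at 94.2%.

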2.7 Analysis of secondary objectives

Except the HAQ-DI[®] score, the secondary efficacy variables are composite endpoints defined in a similar fashion as the primary endpoint and are listed below. Secondary efficacy variables will be analyzed using the FAS population unless otherwise specified.

- **Monotherapy** PASI90 response at Week 52 in Superiority test for secukinumab 300 mg based on Psoriasis subset
- **Monotherapy** ACR50 response at Week 52 in Superiority test for secukinumab 300 mg
- Change from baseline in HAQ-DI[®] score at Week 52 in Superiority test for secukinumab 300 mg based on a MMRM model.
- **Monotherapy** resolution of enthesitis based on LEI at Week 52 in Superiority test for secukinumab 300 mg based on Enthesitis subset (LEI).

All the monotherapy responses (binary endpoints) in the list of the secondary endpoints (PASI90, ACR50, resolution of enthesitis) are defined as meeting the following three conditions:

1. achieving the corresponding clinical response as defined after Figure 2-1
2. no permanent study treatment (Secukinumab or adalimumab) discontinuation before Week 52
3. no use of cDMARDs (including MTX) after week 36 (regardless of taking time of taking cDMARDs).

For HAQ-DI[®] score, if a subject does not meet any of the conditions 2 and 3 above, then the data of this score after the time of taking cDMARDs (including MTX) or premature discontinuation of study treatment will be set to missing (censored) and analyzed using MMRM. For analyses of HAQ-DI[®] score using MMRM, if baseline value is missing then this subject will be removed from the, i.e. it might be that the number of subjects providing data to an analysis is smaller than the number of subjects in the FAS.

Testing strategy to control type I error

The following hypotheses will be included in the hierarchical testing strategy, and type-I-errors will be set such that family-wise two-sided type-I-error of 5% is kept. The inferential testing procedure will only continue if the previous test was rejected at two-sided 5% level.

Primary objective

- H₁: secukinumab 300 mg is not different to adalimumab regimen with respect to monotherapy ACR20 response at Week 52.

[figure not shown]
Secondary objectives

The same method of imputation for binary endpoints that is being used for the primary is also being used for secondary endpoints

- H₂: secukinumab 300 mg is not different to adalimumab regimen with respect to monotherapy PASI90 response at Week 52
- H₃: secukinumab 300 mg is not different to adalimumab regimen with respect to monotherapy ACR50 response at Week 52
- H₄: secukinumab 300 mg is not different to adalimumab regimen with respect to the change from baseline in HAQ-DI[®] at Week 52
- H₅: secukinumab 300 mg is not different to adalimumab regimen with respect to monotherapy resolution of enthesitis based on LEI at Week 52

The graphical approach of ([Bretz et al 2009](#)) for sequentially reject testing procedures is used to illustrate the testing strategy:

Figure 2-1 Hierarchical testing strategy

The family-wise error rate will be set to two-sided $\alpha=5\%$ and it will be controlled with the proposed hierarchical testing strategy. If H1 is rejected at α , each of the following hypotheses will be tested at α . If H2 is rejected at α , H3 will be tested at α and so on.

Monotherapy ACR50 at Week 52

Monotherapy response at Week 52 to ACR50 in the FAS will be evaluated using a logistic regression model with treatment as a factor and weight as a covariate.

Monotherapy PASI90 response

[figure not shown]
Monotherapy PASI90 response at Week 52 will be evaluated using a logistic regression model with treatment as a factor and weight as a covariate based on Psoriasis subset.

Physical function (HAQ-DI[®])

Between-treatment differences in the change in HAQ-DI[®] will be evaluated using a MMRM with treatment regimen, analysis visit as factors, and weight and baseline HAQ-DI[®] score as continuous covariates. Treatment by analysis visit and baseline by analysis visit will be included as interaction terms in the model. An unstructured covariance structure will be assumed for this model. The significance of the treatment effects for secukinumab regimen at different analysis visits will be determined from the pairwise comparisons performed between secukinumab regimen and adalimumab at the appropriate analysis visits.

Monotherapy Resolution of enthesitis

Monotherapy resolution of enthesitis based on LEI at Week 52 will be evaluated using a logistic regression model with treatment as a factor and weight as a covariate based on Enthesitis subset (LEI).

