9.5 Analysis of secondary variables

9.5.1 Efficacy variables

The secondary efficacy endpoints are listed below. Secondary efficacy endpoints will be analyzed using the FAS population unless otherwise specified.

- PASI90 response at Week 52 in Superiority test for secukinumab 300 mg
- ACR50 response at Week 52 in Superiority test for secukinumab 300 mg
- Change from baseline in HAQ-DI[©] score at Week 52 in Superiority test for secukinumab 300 mg
- Resolution of enthesitis at Week 52 in Superiority test for secukinumab 300 mg

Testing strategy

The following hypotheses will be included in the hierarchical testing strategy, and type-I-errors will be set such that family-wise two-sided type-I-error of 5% is kept. The inferential testing procedure will only continue if the previous test was rejected at the appropriate type-I-error rate as specified after Figure 9-1.

Primary objectives (detailed in Section 9.4.2)

[figure not shown]
• H₁: secukinumab 300 mg is not different to adalimumab regimen with respect to ACR20 response at Week 52.

Secondary objectives

The same method of imputation for binary endpoints that is being used for the primary is also being used for secondary endpoints

- H₂: secukinumab 300 mg is not different to adalimumab regimen with respect to PASI90 response at Week 52
- H₃: secukinumab 300 mg is not different to adalimumab regimen with respect to ACR50 response at Week 52
- H₄: secukinumab 300 mg is not different to adalimumab regimen with respect to the change from baseline in HAQ-DI[©] at Week 52
- H₅: secukinumab 300 mg is not different to adalimumab regimen with respect to resolution of enthesitis at Week 52

Figure 9-1 Testing Strategy

- The family-wise error rate will be set to two-sided α =5% and it will be controlled with the proposed hierarchical testing strategy.
 - If H1 is rejected at α , the hypothesis H2 will be tested at α . If H2 is rejected at α , H3 will be tested at α and so on.

ACR50 at Week 52

Response at Week 52 to ACR50 in the FAS will be evaluated using a logistic regression model with treatment as a factor and weight as a covariate.

PASI90 response

[figure not shown]
PASI90 response at Week 52 will be evaluated using a logistic regression model with treatment as a factor and weight as a covariate.

Physical function (HAQ-DI[©])

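### One sentence in SAP 2.7, read literally, opens H2–H5 together once H1 is rejected; it contradicts the fixed sequence stated around it and should revert to the protocol wording

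*SAP*

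**What the plan says.** Five hypotheses are ordered: H1 ACR20, H2 PASI90, H3 ACR50, H4 change in HAQ-DI, H5 resolution of enthesitis. Both documents set a family-wise two-sided error of 5%.

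Protocol 9.5.1 gives the release rule step by step. Once H1 is rejected, "the hypothesis H2 will be tested at α . If H2 is rejected at α , H3 will be tested at α and so on".

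SAP 2.7 opens its testing strategy with the same idea: "The inferential testing procedure will only continue if the previous test was rejected at two-sided 5% level". After Figure 2-1 it says of the family-wise error that "it will be controlled with the proposed hierarchical testing strategy". The next sentence reads "If H1 is rejected at α , each of the following hypotheses will be tested at α". The sentence after that returns to the chain: if H2 is rejected, "H3 will be tested at α and so on".

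SAP Section 1 says the data will be analysed according to protocol section 9, with deviations documented. SAP Section 4 lists no change from the protocol analyses.

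**The concern.** Where the protocol opens one hypothesis after H1, the SAP sentence opens every one that follows. Taken alone, that is a gatekeeper on H1 followed by four parallel tests with no split of alpha. Such a procedure does not keep the 5% family-wise error. It also makes H2, H3 and H4 irrelevant as gates, which the adjacent sentences say they are.

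The two rules part company whenever an earlier secondary fails and a later one has p < 0.05. Suppose H1 and H2 are rejected, ACR50 gives p = 0.08 and HAQ-DI gives p = 0.01. Under the fixed sequence, testing stops at ACR50 and neither HAQ-DI nor enthesitis can be claimed. Under the literal sentence HAQ-DI can be claimed, and so can enthesitis if its own p-value is below 0.05. What is at stake is which secondary results count as confirmatory.

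**Working it through.** **Inputs.** Two-sided alpha of 0.05 (SAP 2.7). Four hypotheses after H1. Effects from SAP Table 3-1 (the same as protocol Table 9-1), with 425 per arm, and 213 per arm for PASI90 and enthesitis (footnote to SAP Table 3-2). The correlation between test statistics is not given; the Table 3-2 footnote says power ignores dependence. I assume a common correlation ρ and show a range.

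**1. The plan's own figures.** For two proportions, with n per arm, p̄ their mean, q = 1 − p and q̄ = 1 − p̄:

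power = Φ{ [|p1 − p0| − 1.96·√(2p̄q̄/n)] / √[(p1q1 + p0q0)/n] }

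- ACR20, 62% vs 50%, n = 425: (0.12 − 1.96 × 0.03405) / 0.03380 = 1.576, so 94.2% (stated 94%).
- ACR50, 49% vs 38%, n = 425: (0.11 − 1.96 × 0.03401) / 0.03380 = 1.282, so 90.0% (stated 91%).
- HAQ-DI, difference 0.19, SD 0.5: 0.19 / (0.5·√(2/425)) − 1.96 = 3.58, so above 99.9% (stated 99%).
- PASI90 and enthesitis, n = 213: both above 99.9% (stated 99%).

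**2. Fixed sequence.** Take the first true null in the order H1 to H5. No type I error can occur unless that hypothesis is rejected, and it is tested at 0.05. The family-wise error is therefore at most 5%. Simulation with H1 always rejected and H2–H5 null gave 5.0% at ρ = 0, 0.3, 0.4 and 0.5.

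**3. Literal reading, H1 false and always rejected, H2–H5 all null.** Independent tests give 1 − 0.95⁴ = 1 − 0.8145 = 18.5%. The bound under any dependence is 4 × 0.05 = 20%. For correlation ρ, with c = 1.96:

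error = 1 − ∫ {Φ[(c − √ρ·x)/√(1−ρ)] − Φ[(−c − √ρ·x)/√(1−ρ)]}⁴ φ(x) dx

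| ρ | H1 always rejected | H1 at its planned 94% power |
|---|---|---|
| 0 | 18.5% | 17.5% |
| 0.3 | 17.4% | 16.0% |
| 0.5 | 15.6% | 13.5% |
| 0.8 | 11.4% | 8.2% |
| 0.9 | 9.4% | 5.9% |

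The last column is simulated with 1,000,000 runs, with H1 sharing the same correlation. If H1 is also null, the H1 gate holds the error at 5.0% even under the literal reading. The inflation does not need all four nulls: with H2 truly effective at its planned power and only H3–H5 null, simulation gives about 13.5% (ρ = 0) and 10.8% (ρ = 0.5).

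**4. How often the two rules would permit different claims.** Now take all Table 3-1 effects as true. The main route is H1 and H2 rejected, ACR50 missed, and a later endpoint significant. Under independence that is 0.942 × 0.9995 × (1 − 0.900) × about 1 = 9.4%. Simulation of all routes gives 9.2–9.4% at ρ = 0, 8.5–8.6% at 0.3, 7.7–7.9% at 0.5 and 6.0% at 0.8, depending slightly on whether a pooled or unpooled variance is used. More than 99% of these cases are the ACR50 miss.

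**The case against.** The strongest reply is that the documents already settle the rule. SAP 2.7 makes each test conditional on the previous rejection, calls the strategy hierarchical, and follows the disputed sentence with a line making H3 depend on H2. That line would be pointless if H3 were already open. The disputed words can be read as each hypothesis in turn, at undivided alpha, and only that reading gives every sentence effect. SAP Section 1 defers to protocol section 9, and SAP Section 4 lists no change. All of this stands as evidence of intent.

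A reader might infer something stronger: that the SAP moved to parallel testing without declaring it, or that the trial runs at a family-wise error of about 16%. The documents support neither. Nothing shows a deliberate change of rule. A figure near 16% needs a correlation that the documents do not give (about 0.45 to 0.5 with H1 always rejected, or about 0.3 with H1 at 94% power), as well as H1 false and all four secondaries exactly null.

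It is also fair to say that the 6% to 9% figure counts trials in which every effect is real. It measures how often the wording would decide what may be claimed, not how often a false claim is made.

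Figure 2-1 is not shown in the text available. Its arrows might confirm the sequence, so nothing here rests on it.

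What the reply does not remove is the contradiction. Two adjacent sentences in the confirmatory rule still give different conditions for testing H3, H4 and H5, and a reader has to infer which governs.

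**Conclusion.** The point holds as a wording defect of minor severity. One SAP sentence, read literally, conflicts with protocol 9.5.1 and with the SAP text on either side of it. The fixed sequence is evidently intended, and under it the claim that "family-wise two-sided type-I-error of 5% is kept" is correct.

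If the literal sentence were followed, with H1 false and rejected and H2–H5 all null, the family-wise error would be roughly 9% to 18.5% for assumed correlations of 0.9 down to 0, and never above 20%. It would be somewhat lower allowing for 94% power on H1, and 5% if H1 were null too. On the plan's own effect sizes, the two readings would permit different claims in about 6% to 9% of trials, for correlations of 0.8 down to 0. These figures show why the sentence should be corrected. They do not describe the error rate of the trial as planned.

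**What to change.** In SAP 2.7, replace the disputed sentence with the protocol's form: if H1 is rejected at α, "the hypothesis H2 will be tested at α". Keep the sentence that follows it. Then add a stopping rule in plain terms: *testing stops at the first hypothesis not rejected in the order H1, H2, H3, H4, H5, and all later p-values are nominal.* Check that the arrows in Figure 2-1 show the same single chain.

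The cost is two sentences of SAP text before unblinding. The sample size, data collection and endpoint models do not change. A later secondary with p < 0.05 could not be claimed after an earlier failure, but the protocol already imposes that limit.
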